- ✤ This is a clinician-rated instrument with 21 items scored on a 0 to 4 scale.
- ✤ Collected at all visits.

As secondary measures to assess severity and improvement relative to baseline for mania, depression and common comorbid conditions, we will use other measures including: a DSM-IV Mania Symptom Checklist; the Attention Deficit Hyperactivity Disorder (ADHD) Rating Scale; the Brief Psychiatric Rating Scale (BPRS); and the NIMH Clinical Global Impression scale (CGI) (Severity, Improvement and Efficacy Index) for mania, depression, Bipolar Disorder overall, ADHD, Oppositional Defiant Disorder and Anxiety. Most of these scales will be administered at baseline visit, at each of the weekly visits and at endpoint by the clinician to assess the impact of treatment on ADHD, anxiety, and to have other measures related to the impact of treatment on bipolar disorder. We will also have the subject's parent/guardian complete the Social Responsiveness Scale (SRS) and the Behavior Rating Inventory of Executive Function – Parent Form (BRIEF) at the Baseline Visit and Week 12 visit.

A. DSM-IV Mania Symptom Checklist

- This Checklist is adapted from the DSM-IV mania diagnostic criteria with items for each symptom of mania. Each item is scored 0 to 3 ranging (0=never or rarely; 1=sometimes; 2=often; 3=very often).
- Collected at baseline visit, at each of the weekly visits and at endpoint as an additional measure of manic symptoms.

B. Attention Deficit Hyperactivity Disorder (ADHD) Rating Scale

The ADHD Rating Scale is an 18-item scale with 1 item for each of the 18 DSM-IV ADHD symptoms. Each item is scored 0 to 3 (0=never or rarely; 1=sometimes; 2=often; 3=very often).

 Collected at baseline visit, middle and endpoint to assess the impact of treatment on ADHD symptoms, which often co-occur with pediatric bipolar disorder.

C. Brief Psychiatric Rating Scale (BPRS)

- The Brief Psychiatric Rating Scale (BPRS) is a common scale used to assess overall psychopathology (Overall & Pfefferbaum, 1982). The scale consists of 18 items; each rated on a scale from 1 (symptom not present) to 7 (symptom extremely severe).
- Collected at Baseline Visit and at endpoint to assess the impact of treatment on depression, anxiety hallucinations and unusual behavior, which often co-occur with pediatric bipolar disorder.

D. Social Responsiveness Scale (SRS)

- The SRS is a 65 item rating scale completed by the parent or guardian. This scale measures the severity of autism spectrum symptoms as they occur in natural social settings.
- Collected at Screening and Endpoint visits as assessment of symptoms and capacities associated with social interaction.

E. NIMH Clinical Global Improvement scale (CGI)

- The CGI is a measure of illness severity adapted for specific disorders. It allows rating of mania, depression and overall bipolar disorder illness, as well as other conditions frequently comorbid with bipolar disorder.
- The severity score ranges from 1 (normal, not at all ill) to 7 (among the most extremely ill patients). The improvement score ranges from 1 (very much improved) to 7 (very much worse).
- Collected at Baseline Visit, at each of the weekly visits and at endpoint as an accepted measure of clinician rated improvement to assess the impact of treatment on bipolar disorder and other comorbid conditions.

F. Behavior Rating Inventory of Executive Function – Parent Form (BRIEF)

- The BRIEF is an 86-item rating scale to assess level of executive function deficits (Roth, Isquith, & Gioia, 2004). It is completed by the subject's parent/guardian.
- Collected at Baseline Visit and at the Week 12 visit for subjects who complete the study.

G. MGH Autism Spectrum Disorder Rating Scale (MGH-ASD-RS-I)

- This is a 37-item scale that asks informants to rate subjects on their social competence and abilities on a Likert scale from 0 to 6.
- Collected at Baseline and Endpoint visits.

Safety Measures

 Adverse Experiences: to record any adverse health events experienced during the study along with duration, severity, cause, remedy, and outcome.

Columbia Suicide Severity Rating Scale (C-SSRS): to assess initial and emergent suicidality.

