Vital signs (blood pressure, pulse, temperature), height, and weight will be measured at every office visit. A urine drug screen will be performed for all subjects aged 12 and over at the screening visit. For female subjects who have begun menstruating, a urine pregnancy test will be performed at the screening visit, followed by a serum pregnancy test if the urine test is positive. If a participant has a positive serum pregnancy test, the study doctor will inform the subject, and she will not be able to take part in the study. The decision whether to inform the parent of these results will be made by the physician based on the participant's age and maturity level and the requirements of the law, unless the participant agrees to parental notification.

Those subjects who terminate study participation before the completion of the study will be asked to complete all tasks scheduled to take place on the final study visit at the time of study discontinuation; however, if the subject refused to complete any portions of the cognitive assessment at baseline, or if the subject was not yet exposed to the study treatments, it is possible that we will not ask him/her to complete these tasks at endpoint, per clinician judgment. Medication compliance for the study will be assessed at each study visit after Baseline.

Dosing

We plan to treat subjects with the following dose:

Subjects ages 5-12 Week 1: 900mg po daily Weeks 2+: 900mg po QAM, 900mg po QPM

Subjects ages 13-17 Week 1: 900mg po daily Week 2: 900mg po QAM, 900mg po QPM Weeks 3+: 1800mg po QAM, 900mg po QPM

In Weeks 3-12 for subjects ages 13-17, we will encourage twice per day dosing, but we will

permit daily dosing if needed for adherence.

The rationale for the NAC dosing is based on two pilot clinical trials and one case report indicating that oral dose of NAC in the range of 800-2700mg is well-tolerated in children (Ghanizadeh & Derakhshan, 2012; Ghanizadeh & Moghimi-Sarani, 2013; Hardan et al., 2012). Hardan and colleagues' (2012) use of increasing doses of NAC in the range of 900-2700mg appears to have been more efficacious than Ghanizadeh's and Moghimi-Sarani's (2013) dosing of 1200mg per day. Therefore, we decided upon an age-appropriate forced titration dosing within the 900-2700mg range, which has been shown to be safe for children.

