14. POTENTIAL BENEFITS

To the Subject

The study will offer rapid access to treatment and provide subjects with a free detailed psychiatric and cognitive evaluation. Subjects will be provided with a potentially useful treatment, which has low risks associated with it.

To Others

The study will further our understanding of the treatment of bipolar disorder in children by testing a novel treatment, N-acetylcysteine. This study will also be useful in the testing of specific hypotheses about the efficacy of alternative treatments.

Importance of the Knowledge to be Gained

Little is known about the treatment of pediatric bipolar disorder, despite the fact that it is recognized as a significant public health concern. This study will further our knowledge regarding potentially useful treatments. As parents are often concerned about the effect of pharmaceutical agents on growth and development, this study examines the efficacy of a safe, alternative treatment that will be appealing to parents and children, due to its safety profile and benign side effect profile. From a scientific perspective, this study also furthers our understanding of the role of NAC in psychiatric disorders.

Visit	99 ¹	0 ²	1	2	3	4	5	6	7	8	9	10	11	12
Consenting														
Parental Consent & Child Assent	Χ													
Procedures														
Physical Examination	Χ													Χ
Vital Signs, Height, Weight	Χ	Χ	Χ	Χ	Χ	Χ				Χ				Χ
Cognitive Tasks														
Cognitive Tasks: IQ Measures (WASI-II or KBIT-2)	X													
Cognitive Tasks: EF Measures (WISC-IV or WPPSI-III)	X													X
Clinician Assessments/Rating Scales														
Clinician K-SADS-E (MDD, Mania)	Χ													
YMRS	Χ	Χ	Χ	Χ	Χ	Χ	Χ	Χ	Χ	Χ	Χ	Χ	Χ	Χ
Mania Symptom Checklist		Χ	Χ	Χ	Χ	Χ	Χ	Χ	Χ	Χ	Χ	Χ	Χ	Χ
CGIs (Mania, Depression, Anxiety, ADHD,		Χ	Х	Х	Х	Х	Х	Х	Х	Х	Х	Х	Χ	Χ
ODD, BPD)														
CDRS	Χ	Χ	Χ	Χ	Χ	Χ	Χ	Χ	Χ	Χ	Χ	Χ	Χ	Χ
HAM-D	Χ	Χ	Χ	Χ	Χ	Χ	Χ	Χ	Χ	Χ	Χ	Χ	Χ	Χ
CSSRS	Χ	Χ	Χ	Χ	Χ	Χ	Χ	Χ	Χ	Χ	Χ	Χ	Χ	Χ
ADHD Rating Scale		Χ						Χ						Χ
BPRS		Χ						Χ						Χ
GAF		Χ	Χ	Χ	Χ	Χ	Χ	Χ	Χ	Χ	Χ	Χ	Χ	Χ
Adverse Events		Χ	Χ	Χ	Χ	Χ	Χ	Χ	Χ	Χ	Χ	Χ	Χ	Χ
Concomitant Medications		Χ	Χ	Χ	Χ	Χ	Χ	Χ	Χ	Χ	Χ	Χ	Χ	Χ
Parent Assessments/Rating Scales														
K-SADS Face Page	Χ													
CBCL	Χ													
FES	Χ													
SAICA	Χ													Χ
PQ-LES-Q		Χ												Χ
BRIEF Parent		Χ												Χ
SRS	X													Χ
MGH-ASD-RS-I		Χ												Χ

Table 1 Schedule of Events

 1 99 – Screening visit(s)

 2 0 – Baseline visit

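### The BRIEF entry limits the endpoint form to completers, against the protocol's own early-termination rule; if followed, treated subjects who leave early have no post-baseline BRIEF.

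*Combined protocol and SAP*

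**What the plan says.** Three places in the combined protocol and SAP bear on who gives an endpoint BRIEF, and a fourth on its analysis.

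- **Section 8, secondary measures, item F (BRIEF).** The entry reads "Collected at Baseline Visit and at the Week 12 visit for subjects who complete the study". The paragraph that introduces the secondary measures gives the same two time points without the restriction: "BRIEF) at the Baseline Visit and Week 12 visit".
- **Section 7, the paragraph on early termination (before Dosing).** Subjects who stop before the end "will be asked to complete all tasks scheduled to take place on the final study visit at the time of study discontinuation". Two exceptions follow, each at the clinician's judgment. One applies "if the subject refused to complete any portions of the cognitive assessment at baseline". The other concerns someone who leaves before any dose: "if the subject was not yet exposed to the study treatments".
- **Table 1.** The BRIEF Parent row is marked at Visits 0 and 12 only, with no footnote about completers.
- **Section 9A.** Baseline is compared with the last assessment, glossed as week 12, by Wilcoxon signed rank tests. No rule is given for missing endpoint data or for early-termination scores.

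**The concern.** At a termination visit, staff have two instructions for the same form. One asks for everything due at the final visit, which on Table 1 includes the BRIEF. The other ties the second BRIEF to completing the study.

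What is at stake is data that cannot be recovered. The YMRS, CDRS and CGI are rated weekly, so a subject who leaves at week 5 still has post-baseline values. The BRIEF has none between baseline and Week 12. If the Section 8 entry is followed, the paired BRIEF change can be computed only in completers. Sections 7 and 10 allow or require subjects to leave for, among other things, poor response, hospitalisation, a worsening course, intolerance or a high suicidality score. Leaving is therefore likely to be related to outcome, and a single-arm paired comparison has no control group whose losses might offset the selection.

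**Working it through.** The plan gives no figure for the BRIEF (no sample size, power or dropout), so there is nothing to reproduce. The check is a comparison of texts, followed by an illustration of size.

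**1. Is the BRIEF a final-visit task?** Yes. Table 1 marks it at Visit 12, so the Section 7 rule for early terminators covers it.

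**2. Do the Section 7 exceptions remove it?** No. One concerns subjects who declined part of the cognitive assessment at baseline. The other concerns subjects who had not started treatment. Neither reaches a treated subject who did the baseline testing and whose parent could fill in a questionnaire.

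**3. Is the restriction part of a pattern?** No. The other parent or informant scales repeated at the end (SAICA, PQ-LES-Q, SRS and MGH-ASD-RS-I) are described in Section 8 as collected at endpoint. The MGH-ASD-RS-I entry, for example, reads "Collected at Baseline and Endpoint visits". Only the BRIEF entry mentions completers, and no reason is given.

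**4. Are other executive-function data affected?** No. Table 1 has a row "Cognitive Tasks: EF Measures (WISC-IV or WPPSI-III"), marked at screening and Visit 12. Section 7, under Weekly Visits, has the cognitive evaluation repeated at the last visit or when a subject drops.

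**5. How large could the effect be if the Section 8 entry is followed?**

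Inputs:
- Completers: 20 (Section 7).
- Treated early leavers, k: not stated, so assumed. The extreme is k = 20, in which all 40 subjects consented and screened are treated.
- Gap g: mean BRIEF improvement in completers minus that in early leavers, in SD units. Not stated, so assumed.

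With Mc and Mt the mean improvements in completers and early leavers:

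all-treated mean = (20·Mc + k·Mt) / (20 + k)

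completer mean − all-treated mean = k·(Mc − Mt) / (20 + k) = [k / (20 + k)] × g

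| k | k/(20+k) | g = 0 | g = 0.25 SD | g = 0.5 SD | g = 1 SD |
|---|---|---|---|---|---|
| 2 | 0.091 | 0 | 0.02 | 0.05 | 0.09 |
| 5 | 0.200 | 0 | 0.05 | 0.10 | 0.20 |
| 10 | 0.333 | 0 | 0.08 | 0.17 | 0.33 |
| 20 | 0.500 | 0 | 0.13 | 0.25 | 0.50 |

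The sign follows g: if early leavers improved more than completers, the completer mean would understate the change. These are differences in means. The planned test is a signed rank test, so the table shows scale and does not predict the test result.

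**The case against.** The best defence is that the Section 8 entry only states timing for subjects who reach Week 12, while Section 7 covers those who do not. The entry does not forbid a form at discontinuation. The introductory paragraph and Table 1, which carry no restriction, support that reading. It is possible, but it leaves the completer phrase with no purpose, and the neighbouring scales manage without one. It does show that the endpoint population is unsettled. A reader might infer that the BRIEF result is completer-only by design; that follows only if the Section 8 entry overrides Section 7, and no text says it does.

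Three other stronger readings also go too far.

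- **That the executive-function result as a whole is completer-only.** The performance tests are to be repeated at drop, so only the parent rating is in question.
- **That those without an endpoint form are the ones doing worst.** Section 7 also lists patient preference, missed appointments, non-compliance, unreturned medication, pregnancy and substance abuse. These need not track executive function.
- **That the completer mean overstates the all-treated mean by 25% to 50%.** That is (20 + k)/20 with k = 5 and k = 10, giving 1.25 and 1.50. Both counts are assumed, and so is zero change in every early leaver. If early leavers change as completers do, the overstatement is nil at any k.

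It is also fair to say that the lack of a missing-data rule is study-wide, that a BRIEF completed at week 2 is not a week-12 value, and that some families will decline the form, since Section 7 only asks. These points limit what the fix can achieve. They do not remove the conflict, and a form never collected cannot be analysed under any rule.

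**Conclusion.** The conflict between the BRIEF entry and the early-termination rule is real, and the Section 7 exceptions do not resolve it. If the BRIEF entry governs, treated subjects who leave early contribute no BRIEF change, and the comparison is completer-only. The bias then probably favours improvement, because several exit reasons are defined by deterioration, but neither direction nor size is established. With 20 completers and an assumed gap of 0.5 SD it is about 0.10 SD for 5 early leavers and 0.17 SD for 10; it is zero if the gap is zero. If Section 7 governs, this source of selection largely disappears, apart from families who decline.

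The reach is limited. The BRIEF is secondary, appears in neither specific aim, and carries no power calculation. The main conclusions on mania and depression do not depend on it. The point still merits a change because it affects data collection, is cheap to settle, and cannot be repaired after subjects have left.

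**What to change.** - In Section 8, item F, replace the completer restriction with wording such as *at Baseline and at Week 12 or at early termination*, in line with Section 7.
- Bring the introductory paragraph on secondary measures into line, and add a footnote to Table 1 saying that the Visit 12 tasks also apply at early termination.
- In Section 9A, state that the BRIEF analysis compares baseline with the last BRIEF in all treated subjects who have a post-baseline form. Report the completer-only result as a sensitivity analysis, with the number of early-termination forms and their timing.

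The cost is one more parent questionnaire at discontinuation, when Section 7 already asks for the other final-visit tasks. The drawback is that early-termination scores reflect shorter exposure, so the main BRIEF result will mix durations; the completer-only analysis shows how much that matters. Subjects whose parents decline the form will still be missing and should be counted.

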10. SAFETY

Consistent with good clinical practice, safety will be monitored by each subject's study clinician at each study visit. This clinician will be available 24 hours a day by page. The Principal Investigator will supervise all study activities including ratings, reported adverse events, laboratory tests, and vital signs. Subjects will be monitored for adverse events at each visit and adverse events will be recorded on an Adverse Events Form. Treatment-emergent adverse events will be monitored through changes in vital signs. All adverse events will be reported according to PHRC guidelines. Blood pressure, pulse, height, weight, and temperature will be recorded at each office visit.

Poor response to treatment will be measured by a CGI-bipolar score that is 2 points higher (more severe) than baseline for 2 weeks in a row or a YMRS score that is 30% higher than baseline for

2 weeks in a row, which may lead to drop from the study as determined by the clinician. Subjects with individual YMRS item scores of 8 on Item #8 (Content), or scores greater than 6 on Disruptive-Aggressive Behavior for 2 weeks in a row will be dropped from the study. In addition, drop from study will occur at clinician discretion for worsening of clinical course, non-compliance with treatment or inability to tolerate study treatment. Finally, the Columbia Suicide Severity Rating Scale (C-SSRS) will be administered weekly to assess initial and emergent suicidality in subjects. Subjects with scores of 4 or higher on the C-SSRS will be dropped from the study.

Having treated hundreds of bipolar patients, we are aware that this is a group of very highly disturbed children at risk for psychosis, suicide and disruption in the family. Although it is unlikely that these risks will be exacerbated by the protocol, we will be vigilant regarding the potential for patient decompensation or dangerousness to self or others. In the execution of research protocols, our primary concern is always the safety of the research participant. [name] has extensive experience in working with youth with severe psychopathology in clinical trials and in designing and implementing safety plans in these trials. Also, [name] is expert in the diagnosis and treatment of pediatric bipolar disorder and high-risk pediatric psychiatry patients in clinical settings. Given the especially unstable nature of bipolar spectrum subjects, we are available to handle clinical emergencies with subjects and their families at any time: at the time of visit, whether in person or over the phone, as well as between visits.

If needed, emergency evaluation and referral is available through coverage by the clinicianinvestigators on this study and through the Acute Psychiatry Service (APS) at the MGH. All subjects will have access to a 24 hour a day, 7-day week coverage provided by [name] or her designated substitute by pager for psychiatric emergencies. As part of the Massachusetts General Hospital, all research subjects can access the Acute Psychiatry Service (APS) in the emergency room at any time of the day or night. The APS is a well-staffed 24 hour/7 day per week emergency service for psychiatric emergencies.

11. CONFIDENTIALITY

All research-related records, initiated as a result of a subject's participation in this study that reveal the subject's identity, will remain confidential except as may be required by law. Subjects will only be contacted regarding future studies if they indicate that they are interested in being contacted by initialing in the specific section of the consent form.

If subjects agree on the Consent Form, we may share subjects' information with others within our research group for future research on emotional dysregulation or other related conditions. We will label all subjects' study materials with a code instead of their names. The study doctor will not share the key to code names with researchers outside of this institution.

12. MONITORING AND QUALITY ASSURANCE

The Principal Investigator is responsible for monitoring the safety and data of this trial. The PI will monitor adherence to the protocol, subject participation (e.g. tolerance to medication, dropout rates, etc.), the risk-benefit ratio, and all Adverse Events throughout the course of the study. The IRB will be informed of any serious adverse events occurring during the trial. If at any time during the study more than 10% of the patients have had a serious adverse event, the study will be stopped. The primary concern of the investigators of this study is the safety of the subjects.

13. RISKS AND DISCOMFORTS

Potential side effects are few and will be monitored for throughout the research study. Consent forms will clearly list potential medication side effects. Since NAC is a derivative of a naturally occurring amino acid, it appears to have a low potential for unwanted side effects or negative effects on the child's growth and development. Although NAC is generally well tolerated, animal (but not human) subjects have developed pulmonary hypertension with high doses. Seizure with NAC has been reported in an accidental overdose of 39,207mg NAC in a 30-monthold girl, more than 10 times the dose she should have received. Seizure has not been reported with recommended dosing (Bailey, Blais, & Letarte, 2004).

The most common side effects reported with use of NAC are gastrointestinal. Other less common side effects that have been reported include fatigue, nervousness, vivid dreams, heartburn, pruritus (without rash), and headaches (Berk, Copolov, Dean, Lu, Jeavons, Schapkaitz, Anderson-Hunt, Judd, et al., 2008; Ghanizadeh & Moghimi-Sarani, 2013; Gray et al., 2012; Hardan et al., 2012; Mardikian, LaRowe, Hedden, Kalivas, & Malcolm, 2007). Serious side effects are uncommon.

Other Adverse Events

Problems and side effects not listed above and not known at this time could occur. Subjects will be told of any changes in the way the study will be done and any newly discovered risks to which they may be exposed.

Answering detailed questionnaires may create a mild degree of inconvenience or emotional upset for the subjects. Interviewers will be trained to support the subjects who raise such concerns, and the PI will be available to respond to any concerns or to answer other questions about the study (available by pager 24 hours per day). All of the information about participants will be treated confidentially. Subjects may refuse to answer any of these questions.

Having treated hundreds of bipolar patients, we are aware that this is a group of very highly disturbed children at risk for psychosis, suicide and disruption in the family. Although it is unlikely that these risks will be exacerbated by the protocol, we will be vigilant regarding the potential for patient decompensation or dangerousness to self or others. In the execution of research protocols, our primary concern is always the safety of the research participant. Given the especially unstable nature of bipolar patients, we will be available to the study staff and to

patients and their families to handle clinical emergencies. The Massachusetts General Hospital has an active and well-staffed psychiatric emergency service that will be available to subjects if needed. This study has clearly defined exit criteria to ensure the safety of participants.

Protection Against Risk

Subjects' confidentiality will be protected throughout the study. Information about subjects and their families will be stored in research files identified only by a code. The code key connecting the participant's names to identifying information will be kept in a separate, secure location. Data in databases is similarly identified only by coded ID number and is password-protected. Data will not leave our institution in any form that would identify individual subjects or families. The information collected in our assessments and treatment outcome rating scales will not become part of the individual's hospital medical record. In the case that serious psychopathology (suicidality, homocidality, psychosis) is uncovered in the course of the research study, the Principal Investigator or appointed proxy will be immediately contacted by the clinician. All efforts will be made to alert parents of the subject and, if necessary, treating clinicians, of the circumstances to enable the subject to secure appropriate treatment. If needed, emergency evaluation and referral will be available through coverage by the clinician-investigators on this study and through the Acute Psychiatry Service (APS) at the MGH. The APS is a well staffed 24 hour/7 day per week emergency service for psychiatric emergencies. Subjects who do not respond to the study treatments will be dropped from the study using clear drop criteria ("patients may drop at any time due to patient preference, physician decision, need for psychiatric hospitalization or a poor response to treatment. Poor response to treatment leading to drop from the study will be measured by a CGI-mania score that is 2 points lower (more severe) than baseline for more than 2 weeks in a row, a YMRS score that is 30% higher than baseline for more than 2 weeks in a row"), or a C-SSRS score of 4 or higher.

